- 6. Sample collected at Day 61 will be used for the post-vaccination RSVPreF3 OA investigational vaccine-related testing.
- AF will be considered as AESI in this study and will be additionally reported in the AF follow-up questionnaire (electronic or paper) in eCRF. The collection of AF will be performed following the AE/SAE reporting periods. The reporting of non-serious AF will be performed according to the unsolicited AE reporting period. The reporting of AF meeting the SAE definition (serious AF) will be performed according to the SAE reporting period.
- 8. SAEs related to study participation, or to a concurrent GSK medication/vaccine should be collected from the time of consent obtained (prior to study vaccine administration) up to study end.

Table 3 Intervals between study visits (Co-Ad group)

Interval	Planned visit interval	Allowed interval range
Visit 1 → Visit 2	30 days	30-42 days
Visit 1 → Contact	180 days	180-210 days

Table 4 Intervals between study visits (Control group)

Interval	Planned visit interval	Allowed interval range
Visit 1 → Visit 2	30 days	30-42 days
Visit 2 → Visit 3	30 days	30-42 days
Visit 2 → Contact	180 days	180-210 days

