•	To evaluate the safety and reactogenicity following administration of the RSVPreF3 OA investigational vaccine and a COVID-19 mRNA vaccine, co-administered or	•	Percentage of participants reporting each solicited administration site event and systemic event within 4 days post study intervention administration (i.e., the day of vaccination and 3 subsequent days).
	administered alone.	•	Percentage of participants reporting unsolicited AEs within 30 days post study intervention administration (i.e., the day of vaccination and 29 subsequent days).
		•	Percentage of participants reporting SAEs after study intervention administration (Day 1) up to study end (6 months after last study intervention administration).
		•	Percentage of participants reporting pIMDs after study intervention administration (Day 1) up to study end (6 months after last study intervention administration).

AE: adverse event; GMC: Geometric Mean Concentration; GMT: Geometric Mean Titer; MGI: Mean Geometric Increase; pIMD: potential immune mediated disease; SAE: serious adverse event, SRR: Seroreponse rate. MGI and SRR are defined in Section 9.3.2.

^{*} Non-inferiority criteria are defined in Section 9.3.1.

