3.2.2. Safety Objectives

The secondary question of interest is to evaluate the safety and reactogenicity following administration of the RSVPreF3 OA investigational vaccine and a dose of COVID-19 mRNA vaccine, co-administered or administered alone.

		Attributes				
Treatment Population		Endpoint (Variable)		Intercurrent ev	Summary measure	
Heatment	i opulation	Enapoint (variable)		Description	Handling strategy	
Co-ad group: COVID- 19 mRNA vaccine at Day 1 and RSVPreF3 OA investigational vaccine at Day 1 Control group: COVID-19 mRNA vaccine at Day 1 and RSVPreF3 OA investigational vaccine at Day 31	Adults ≥50 years at the time of first vaccination	 Occurrence of each solicited administration site event with onset within 4 days after study intervention administration. Occurrence of each solicited systemic event with onset within 4 days after study intervention administration. Occurrence of unsolicited AEs within 30 days after study intervention administration. Occurrence of SAEs after study intervention administration (Day 1) up to study end (6 months after last study intervention administration). Occurrence of pIMDs after study intervention administration (Day 1) up to study end (6 months after last study intervention administration). 	2.	Study vaccination not administered as per protocol. Prohibited medication, vaccination or intercurrent medical condition prior to the blood sample.	All the data collected for the variable of interest are used regardless of whether the intercurrent event occurs (treatment policy).	The percentage of participants by group who report each of the endpoint.

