2050	Intercurrent medical condition: Participants may be eliminated from the PPS for immunogenicity if, during the study, they incur a condition that has the capability of altering their immune response or are confirmed to have an alteration of their initial immune status.	Visit 1 & 2 for Co-ad. Visit 1, 2 & 3 for control group.	RSV PPS, COVID-19 mRNA PPS
2080	Participants did not comply with vaccination schedule for the control group.	Visit 2 for control group	RSV PPS for control group
	 Number of days between COVID-19 mRNA vaccine and RSV vaccine is outside [30-42 days] 		
2090	Participants did not comply with blood sample schedule: For Co-ad and control group: Number of days between vaccination (Visit 1) and blood sample (Visit 2) is outside [30-42] days. For control group: Number of days between vaccination (Visit 2) and blood sample (Visit 3) is outside [30-42] days.	Visit 2, Visit 3	RSV PPS, COVID-19 mRNA PPS
2100	Immunological results not available post-vaccination	Visit 2, Visit 3	RSV PPS, COVID-19 mRNA PPS
2120	Obvious incoherence/abnormality or error in laboratory data Unreliable released data as a result of confirmed sample mismatch or confirmed inappropriate sample handling at laboratory.	Visit 1 & 2 for Co-ad. Visit 1, 2 & 3 for control group.	RSV PPS, COVID-19 mRNA PPS

⁽¹⁾ In case an emergency mass vaccination for an unforeseen public health threat (e.g.: a pandemic) is recommended a1d/or organized by the public health authorities, outside the routine immunization program, the time period described above can be reduced if necessary for that vaccine provided it is used according to the local governmental recommendations and that the Sponsor is notified accordingly.

⁽²⁾ EEC directive 93/42/EEC defines an invasive medical device as 'A device which, in whole or in part, penetrates inside the body, either through a body orifice or through the surface of the body'.

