4.4.1. Adverse Events

An adverse event (AE) is considered study intervention emergent if the AE onset date is on or after study intervention start date. All AE summaries will be based on study intervention emergent events unless otherwise specified. SAE summaries will be based on all SAEs reported regardless of whether they meet the definition of study intervention emergent or not. All AE and SAE summaries will be grouped by SOC, HLT and PT and summarized by study intervention group at time of onset of the AE, unless otherwise specified.

Adverse events will be coded using the standard Medical Dictionary for Regulatory Activity (MedDRA dictionary). The verbatim reports of unsolicited AEs, including SAE and AESI, will be reviewed by a qualified person and the signs and symptoms will be coded according to the MedDRA Dictionary for Adverse Reaction Terminology. Every verbatim term will be matched with the appropriate Preferred Term.

For the summaries of AE and SAE, participants who experience the same AE/SAE (in terms of the MedDRA SOC, HLT and PT) more than once will only be counted once for that event in the number of participants but all occurrences of the same event will be counted in the number of events. Also, in the case of co-administered study interventions, an administration site event recorded for a participant following multiple study interventions will be counted as only one occurrence.

A study intervention-related AE/SAE is defined as an AE/SAE for which the investigator classifies the possible relationship to study intervention as "Yes". A worst-case scenario approach will be taken to handle missing relatedness data, i.e., the summary table will include events with the relationship to study intervention as 'Yes' or missing.

The analyses of unsolicited AEs will include SAEs and AESIs (unless otherwise specified).

The following analysis will be performed:

- Compliance in completing solicited events information will be tabulated after each dose and overall.
- The number and percentage of participants with at least one administration site event (solicited and unsolicited), with at least one systemic event (solicited and unsolicited) and with any AE (solicited and unsolicited) during the 4-day or 30-day follow-up period after vaccination will be tabulated with exact 95% CI for each group, after each dose and overall.

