- The same computations will be done for Grade 3 AEs, for Grade 3 non-serious AEs and for AEs resulting in a medically attended visit.
 - Those analyses will present all solicited and unsolicited AEs, including SAEs and AESIs (unless otherwise specified).
- The number and percentage of participants with at least one administration site event (solicited only), with at least one systemic event (solicited only) and with any solicited event during the 4-day follow-up period after vaccination will be tabulated with exact 95% CI for each group, after each dose and overall.
- The same computations will be done for Grade 3 AEs and for AEs resulting in a medically attended visit.
- The number and percentage of participants reporting each individual solicited administration site or systemic event (any grade, Grade 3 and resulting in medically attended visit) during the 4-day follow-up period after vaccination will be tabulated with exact 95% CI for each group, after each dose and overall.
- For fever, the number and percentage of participants reporting fever by half degree (°C) cumulative increments during the 4-day follow-up period after vaccination will be tabulated for each group, after each dose and overall.
- The percentage of participants with each solicited administration site event and solicited systemic event (any grade and Grade 3) during the 4-day follow-up period after vaccination will be represented graphically for each group after each dose and overall.
- The duration in days of each individual solicited events will be tabulated using descriptive statistics (mean, min, Q1, median, Q3, maximum).
- The number of days with Grade 3 solicited events will be tabulated for each individual solicited event using descriptive statistics (mean, min, Q1, median, Q3, maximum).

- The number and percentage of participants with any unsolicited AEs during the 30-day follow-up period (i.e., the day of vaccination and 29 subsequent days) with its exact 95% CI will be tabulated by group and by Medical Dictionary for Regulatory Activities (MedDRA) Primary System Organ Class (SOC), High Level Term (HLT) and Preferred Term (PT), after each dose and overall. Similar tabulation will be done for Grade 3 unsolicited AEs, for any causally related unsolicited AEs, for Grade 3 causally related unsolicited AEs and for unsolicited AEs resulting in a medically attended visit.

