- The number and percentage of participants with any non-serious unsolicited AEs during the 30-day follow-up period with its exact 95% CI will be tabulated by group and by MedDRA Primary System Organ Class (SOC), High Level Term (HLT) and Preferred Term (PT), after each dose and overall. Similar tabulation will be done for Grade 3 non-serious unsolicited AEs, for any causally related non-serious unsolicited AEs and for non-serious unsolicited AEs resulting in a medically attended visit.
- The number and percentage of participants with any unsolicited AEs reported within 30 minutes following vaccination with its exact 95% CI will be tabulated by group and by MedDRA Primary System Organ Class (SOC), High Level Term (HLT) and Preferred Term (PT), after each dose and overall. Similar tabulation will be done for Grade 3 unsolicited AEs reported within 30 minutes following vaccination.
- The number and percentage of participants with at least one report of SAE classified by the MedDRA Primary SOC, HLT and PT from vaccination up to study end (i.e., 6 months after last vaccination) will be tabulated with exact 95% CI.
- The same tabulation will be presented for causally related SAE, fatal SAE, pIMD and causally related pIMD.
- All SAEs/AESIs up to study end (i.e., 6 months after last vaccination) will also be described in detail in a tabular listing.
- AEs/SAEs leading to study discontinuation from vaccination up to study end will be tabulated.
- For web posting purposes, the number of occurrences and the number and percentage of participants with non-serious AEs (solicited and unsolicited combined) during the 30-day follow-up period (i.e., the day of vaccination and 29 subsequent days) will be produced by SOC and PT.
- In case of pregnancies, these will be described in detail.

For analysis of SAEs/AESIs within 6 months, the reporting period will start at vaccination and will end at Day 183 after each dose, computed as 6 x 30.5 days = 183 days.

Refer to Section 6.1.4 and Section 6.1.5 for the analysis of concomitant medications and concomitant vaccination.

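### SAE, fatal SAE and pIMD percentages cover 30 to 42 more days in on-schedule Control participants than in Co-Ad, with no person-time rate beside them; the age-subgroup unsolicited AE table and the two web-posting tables specify no per-dose columns

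*SAP*

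**What the plan says.** **Endpoint.** Protocol 3.1 defines the SAE endpoint as "Percentage of participants reporting SAEs after study intervention administration (Day 1) up to study end (6 months after last study intervention administration"; the pIMD endpoint has the same form. Protocol 3.2.2 gives the summary measure as "The percentage of participants by group who report each of the endpoint".

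**SAE and pIMD tables.** SAP 4.4.1 tabulates participants with at least one SAE "from vaccination up to study end (i.e., 6 months after last vaccination) will be tabulated with exact 95% CI". Related SAEs, fatal SAEs, pIMDs and related pIMDs follow the same layout. The bullets for these tables do not mention a split by dose. The same section adds that, for SAEs and AESIs within 6 months, "the reporting period will start at vaccination and will end at Day 183 after each dose", computed as 6 x 30.5 days. It names no table for that window.

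**Timing.** The visit-interval tables in Protocol 1.3 put the final contact 180 to 210 days after Visit 1 in Co-Ad and 180 to 210 days after Visit 2 in Control. Visit 2 is 30 to 42 days after Visit 1. Protocol 4.1 gives study durations of about 6 and about 7 months.

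**AE tables.** The main unsolicited AE table in SAP 4.4.1 is by "High Level Term (HLT) and Preferred Term (PT), after each dose and overall", and the main solicited tables have the same split. In SAP 4.5.1.2 the age-subgroup solicited table has it too. The age-subgroup unsolicited table does not, nor do the web-posting tables in 4.4.1 and 4.5.1.2. The default in 4.4.1, "summarized by study intervention group at time of onset of the AE, unless otherwise specified", sets the group and does not create dose columns.

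**The concern.** Background events accumulate with time. If two groups have the same underlying risk and one is watched for longer, the longer-watched group shows the higher percentage. Here that is Control, so the crude table makes co-administration look slightly safer than it is. In a study meant to compare giving the vaccines together with giving them apart, that direction can mask a difference. Neither document plans a rate per time at risk that would let a reader see how much of a difference comes from the window.

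The three tables without per-dose columns have the same problem in another form. Control contributes two 30-day follow-up periods and Co-Ad one, and the table itself does not let the reader separate them.

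**Working it through.** **Inputs.**
- Dose gap in Control, g: 30 to 42 days (Protocol 1.3).
- Last dose to final contact, L: 180 to 210 days (Protocol 1.3).
- Six-month period: 183 days (SAP 4.4.1).
- Group size: 415 (Protocol 9.5).
- The documents give no event rates, so every risk below is an assumption.

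**The plan's own figure.** 6 x 30.5 = 183 days; reproduced.

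**Length of observation.** By the 183-day figure, Co-Ad has 183 days. Control has 183 + 30 = 213 to 183 + 42 = 225 days. The ratios are 213/183 = 1.164 and 225/183 = 1.230.

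By actual contact, Co-Ad has 180 to 210 days and Control 210 to 252. At the same L in both groups the ratio is (L + g)/L:
- L = 180: 210/180 = 1.167 and 222/180 = 1.233.
- L = 210: 240/210 = 1.143 and 252/210 = 1.200.

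**Effect on the percentage.** With the same constant hazard in both groups and a Co-Ad risk p over 183 days, the Control risk is 1 - (1 - p)^((183 + g)/183). Extra Control participants = 415 x (Control risk - p).

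| Assumed p | Control, g = 30 | Extra of 415 | Control, g = 42 | Extra of 415 |
|---|---|---|---|---|
| 1% | 1.16% | 0.68 | 1.23% | 0.95 |
| 3% | 3.48% | 2.01 | 3.68% | 2.80 |
| 5% | 5.80% | 3.30 | 6.11% | 4.61 |

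The 42-day columns need every Control participant to be at the limit of the visit window. For pIMD at assumed risks of 0.3% and 0.5%, the excess is 0.20 and 0.34 participants (g = 30), or 0.29 and 0.47 (g = 42).

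**Does a rate remove it?** At p = 3% and equal hazard, Co-Ad expects 12.45 first events in 204.8 person-years. Control expects 14.46 in 237.8 (g = 30) or 15.25 in 250.9 (g = 42). All three give 6.08 per 100 person-years.

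**Does the Day 183 sentence remove it?** No. Applied per dose, Control has two 183-day windows that overlap by 183 - 42 = 141 to 183 - 30 = 153 days. The SAP does not say which dose an event in the overlap counts for. The rule in SAP 6.3.1 covers only events that start on the day of a dose. The two windows combined still span 213 to 225 days.

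**Tables without per-dose columns.** Control pools 2 x 30 = 60 days of follow-up against 30 in Co-Ad. As an illustration for unsolicited AEs only, let p be the Co-Ad 30-day incidence, H = -ln(1 - p), and f the share of that hazard that is background. Then Control = 1 - exp(-(1 + f)H), provided that vaccine-caused risk has the same total in both groups.
- f = 0.25: p = 10% gives 12.3% (ratio 1.23); p = 30% gives 36.0% (1.20).
- f = 0.5: p = 10% gives 14.6% (1.46); p = 30% gives 41.4% (1.38).

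This model does not describe the web-posting tables, which mix solicited and unsolicited events, so no size is claimed for them.

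**The case against.** The strongest reply is that the plan does what the protocol declares. The percentage to 6 months after the last dose is the defined endpoint for two regimens that differ in length by design. No safety hypothesis is tested. The whole-population 30-day AE tables already have equal per-dose windows, and all SAEs and AESIs are listed individually. This stands. It is why the percentages should stay and why the point is small.

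A second reply is that a person-time rate has a bias of its own. Suppose Co-Ad has 6 background and 4 vaccine-related events in 183 days, and the vaccine-related number is the same in Control. With a 30-day gap, Control has 6 x 213/183 + 4 = 10.98 events. The crude Control/Co-Ad ratio is 10.98/10 = 1.10, which favours Co-Ad. The Co-Ad/Control rate ratio is (10/183)/(10.98/213) = 1.06, which goes slightly against Co-Ad. This also stands: the rate belongs beside the percentage, not in its place. It will also be imprecise. Four events in about 208 person-years give 1.9 per 100, with an exact 95% CI of 0.5 to 4.9.

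A reader might infer more than the documents support:
- That all age-subgroup AE tables lack per-dose columns. The solicited one has them.
- That every Control participant is observed 30 to 42 days longer. Someone who never receives the RSV dose has no later last vaccination. Elimination code 2080, "Number of days between COVID-19 mRNA vaccine and RSV vaccine is outside [30-42 days", does not bound the gap either: it applies to the RSV per-protocol set, while safety uses the Exposed Set. The range rests on the visit schedule.
- That the contact-based difference is always 30 to 42 days. If the time to contact differs between groups, it can run from 210 - 210 = 0 to 252 - 180 = 72 days.

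**Conclusion.** The point holds as a modest reporting gap, worth considering. For Control participants dosed on schedule, the SAE, fatal SAE and pIMD percentages cover 30 to 42 more days than in Co-Ad. Under an equal constant hazard this inflates the Control percentage by a factor of 1.14 to 1.23. At assumed SAE risks of 1% to 5% and the planned 30-day gap, that is about 0.7 to 3.3 participants of 415; for pIMD it is less than one. The direction favours Co-Ad.

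It might be inferred that this could overturn a safety conclusion or affect the non-inferiority result. The documents do not support that: the safety endpoints are descriptive, and the primary analyses use immunogenicity data only.

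The missing per-dose wording in three tables is an inconsistency with the SAP's other AE tables. In the age-subgroup unsolicited table, comparing ages within a group is unaffected; only the between-group reading within an age stratum is. The ratios shown for pooled unsolicited AEs depend entirely on the assumed background share and on equal total vaccine-caused risk.

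**What to change.** Keep all planned percentages, and make these changes:

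1. In SAP 4.4.1, add first-event incidence per person-time with an exact Poisson CI for SAE, fatal SAE and pIMD, by group on the Exposed Set. Count time from first dose to first event, withdrawal or end of the reporting period. Show it beside the percentage.
2. Add the per-dose and overall split to the age-subgroup unsolicited AE table in SAP 4.5.1.2 and, where the posting format allows, to the web-posting tables in 4.4.1 and 4.5.1.2.
3. Footnote the overall columns as cumulative over windows of unequal length.
4. State which table uses the Day 183 rule, and how Control events in the overlap of the two windows are attributed.

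Read the results together. The crude percentage leans towards Co-Ad and the rate can lean slightly against it. Per-dose columns set two vaccines in Co-Ad against one in each Control window.

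The cost is a few extra outputs and footnotes from data already collected. The rates average early vaccine-related events with later background events, and their intervals will be wide.

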4.4.1.1. Adverse Events of Special Interest

The following will be considered adverse events of special interest (AESI) for the purpose of analyses:

- Atrial Fibrillation (AF)
- potential Immune Mediated Disease (pIMD)

AF AESIs will be identified through the MedDRA preferred term of interest atrial fibrillation (10003658). Sites will be prompted via query to complete any necessary additional information for these AESIs in the eCRF. Additional analysis might be performed on those additional data collected for AF AESIs.

pIMDs will be identified using a lookup table containing the list of MedDRA preferred term.

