8.4.4.1. Potential immune-mediated diseases

Potential immune-mediated diseases (pIMDs) are a subset of AESIs that include autoimmune diseases and other inflammatory and/or neurologic disorders of interest which may or may not have an autoimmune etiology. AEs that need to be recorded and reported as pIMDs include those listed in the Table 10.

In order to facilitate the documentation of pIMDs in the eCRF, a pIMD standard questionnaire and a list of preferred terms (PTs) and PT codes corresponding to the above diagnoses will be available to investigators at study start.

The investigator(s) must exercise their medical/scientific judgment to determine whether other diseases have an autoimmune origin (i.e., pathophysiology involving systemic or

217848 (RSV OA=ADJ-013) Protocol Final

organ-specific pathogenic autoantibodies) and should also be recorded as a pIMD. In addition, the investigator should categorize each pIMD either as a new onset condition (if it started following vaccination) or as an exacerbation of a pre-existing chronic condition (if it exacerbated following vaccination) in the eCRF.

Table 10 List of potential immune-mediated diseases (pIMDs)

Medical Concept	Additional Notes
Blood disorders and coagulopathie	s
Antiphospholipid syndrome	
Autoimmune aplastic anemia	
Autoimmune hemolytic anemia	Includes warm antibody hemolytic anemia and cold antibody hemolytic anemia
Autoimmune lymphoproliferative syndrome (ALPS)	
Autoimmune neutropenia	
Autoimmune pancytopenia	
Autoimmune thrombocytopenia	 Frequently used related terms include: "autoimmune thrombocytopenic purpura", "idiopathic thrombocytopenic purpura (ITP)", "idiopathic immune thrombocytopenia", "primary immune thrombocytopenia".
Evans syndrome	
Pernicious anemia	
Thrombosis with thrombocytopenia syndrome (TTS)	
Thrombotic thrombocytopenic purpura	Also known as "Moschcowitz-syndrome" or "microangiopathic hemolytic anemia"
Cardio-pulmonary inflammatory dis	orders
Idiopathic	Including but not limited to:
Myocarditis/Pericarditis	Autoimmune / Immune-mediated myocarditis
	Autoimmune / Immune-mediated pericarditis
	Giant cell myocarditis
Idiopathic pulmonary fibrosis	Including but not limited to:
	 Idiopathic interstitial pneumonia (frequently used related terms include "Interstitial lung disease", "Pulmonary fibrosis", "Immune-mediated pneumonitis")
	Pleuroparenchymal fibroelastosis (PPFE)

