4.7. Changes to Protocol Defined Analyses

In the protocol amendment 4 section 9.4.1: the possibility of performing a combined first and end of study (EoS) analysis if the data for the first analysis are not immediately available

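### The SAP identifies pIMDs only by a preferred-term lookup and does not say how an investigator-recorded pIMD outside that list is counted

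*SAP*

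**What the plan says.** Protocol 8.4.4.1 gives two routes to a pIMD.

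- **Listed diagnoses.** Table 10 sets out diagnoses to be recorded and reported as pIMDs. The coding aid for sites is tied to these: "a list of preferred terms (PTs) and PT codes corresponding to the above diagnoses will be available to investigators at study start".
- **Investigator judgment.** The same section adds: "The investigator(s) must exercise their medical/scientific judgment to determine whether other diseases have an autoimmune origin". The sentence goes on to define autoimmune origin and closes with the instruction to record such a disease: "organ-specific pathogenic autoantibodies) and should also be recorded as a pIMD". The investigator also classifies every pIMD in the eCRF as new onset or as an exacerbation.

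SAP 4.4.1.1 gives one route for analysis: "pIMDs will be identified using a lookup table containing the list of MedDRA preferred term".

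SAP 4.4.1 tabulates pIMDs and causally related pIMDs with exact 95% confidence intervals. It also provides a listing: "All SAEs/AESIs up to study end (i.e., 6 months after last vaccination) will also be described in detail in a tabular listing". It does not say whether AESI status in these outputs comes from the lookup, the investigator's record or both. The derivation rules in SAP 6.3 contain nothing on pIMDs. SAP 4.7 declares one departure from the protocol: "the possibility of performing a combined first and end of study (EoS) analysis if the data for the first analysis are not immediately available".

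**The concern.** The data are collected under one definition and analysed under another that may be narrower. The proportion of participants with a pIMD from Day 1 to study end is a secondary safety endpoint (Protocol 3.1; SAP 1.1). Protocol 2.3.1 names pIMDs as a theoretical risk of adjuvanted vaccines and points to 8.4.4.1 as the mitigation. Protocol 4.2 gives the adjuvant as the reason for six months of safety follow-up. An event that a site correctly recorded as a pIMD could be missing from the table built to report pIMDs, and a reader of the report would not know.

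The study is open-label. If the handling of off-list events is left until the analysis, it will be decided by people who may already know the cases and their groups.

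**Working it through.** No stated figure is in dispute, so the main check is a comparison of the texts.

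**1. Is the protocol's definition wider than a term list?** Yes. Protocol 8.4.4.1 presents Table 10 as included examples, many Table 10 entries are themselves open-ended, and the investigator route is mandatory. The term list given to sites corresponds to the tabulated diagnoses, so it does not cover the investigator route. Protocol Table 11 starts the 24-hour pIMD reporting clock when the investigator decides that the event meets the AESI definition. Collection therefore runs on the investigator's decision.

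**2. Does the SAP restore the investigator route anywhere?** No. SAP 4.4.1, 4.4.1.1, 6.3 and 4.7 contain no rule that the investigator's designation counts, and none for resolving a disagreement between list and investigator.

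**3. Where would an off-list, investigator-recorded pIMD appear if SAP 4.4.1.1 is followed literally?**

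| Event | pIMD and related-pIMD tables | Other planned output |
|---|---|---|
| Serious | Omitted | SAE table to study end |
| Non-serious, onset within 30 days of a dose | Omitted | Unsolicited AE tables |
| Non-serious, later onset, leads to withdrawal | Omitted | Table of events leading to study discontinuation |
| Non-serious, later onset, no withdrawal | Omitted | AESI listing, only if AESIs are also flagged from the investigator's record |

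In every row the event is lost from the secondary endpoint. In the last row it may appear in no planned table.

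**4. Does the safety estimand settle it?** No. Protocol 3.2.2 uses all collected data whatever intercurrent events occur. That strategy does not say which events are pIMDs.

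**5. Scale, for illustration only.** The documents give no expected pIMD rate. Assume 415 exposed per group (the planned size in Protocol 4.1) and x participants whose only pIMD is off-list and who are the only cases in the group. Each omitted participant is 1/415 = 0.24 percentage points. The exact (Clopper-Pearson) limits, the SAP's method for proportions, are:

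- lower = 2.5th percentile of Beta(x, 415 − x + 1), or 0 when x = 0
- upper = 97.5th percentile of Beta(x + 1, 415 − x); for x = 0 this is 1 − 0.025^(1/415) = 0.88%

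| x | Percentage under the protocol definition | Exact 95% CI | Reported under the lookup alone |
|---|---|---|---|
| 1 | 0.24% | 0.01 to 1.34% | 0% (upper limit 0.88%) |
| 2 | 0.48% | 0.06 to 1.73% | 0% (upper limit 0.88%) |
| 3 | 0.72% | 0.15 to 2.10% | 0% (upper limit 0.88%) |

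These counts are hypothetical. They show what one to three omissions would do to the reported figure and say nothing about how likely an omission is.

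**The case against.** The strongest reply is that exclusion is inferred. The lookup table is not in the documents and may be wider than Table 10, or may be extended with investigator-recorded terms. SAP 4.4.1.1 does not say that the lookup is the only route. SAP 4.7 declares no change to the pIMD definition, so the protocol's definition may be meant to stand, with the lookup serving to find events that sites did not flag. All of this is possible, but nothing in the text says it, and a programmer following SAP 4.4.1.1 would apply the lookup alone.

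A second reply is that the exposed case is narrow. Table 10 is broad, serious and early events are tabulated elsewhere, and every pIMD is due at the sponsor within 24 hours of the investigator's determination. This stands. It limits the size of the point, but it does not bring an omitted event back into the endpoint.

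A third reply is that a fixed term list is objective and reproducible, which has value in an open-label trial. This also stands in part, and it is the reason to show the source of each classification alongside the combined count.

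**Conclusion.** The concern holds and is minor. The SAP's one stated rule does not implement the protocol's definition of a pIMD and gives no way to resolve a mismatch between list and investigator. Followed exactly, it would drop an off-list, investigator-recorded pIMD from a declared secondary endpoint and from the causally related pIMD table.

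The number of affected events cannot be determined from the documents and may be zero. The conclusion assumes that the lookup is not extended with investigator-recorded terms; if it is, the remaining defect is that the SAP does not say so. The endpoint is descriptive, and the non-inferiority tests, type I error and sample size are not affected. Confidence is medium because the lookup table is not available.

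**What to change.** In SAP 4.4.1.1, state that an adverse event counts as a pIMD if its preferred term is on the lookup table **or** the investigator recorded it as a pIMD in the eCRF. Apply the same rule to the AESI listing, and add a column giving the source (list, investigator or both) so that the list-only count stays visible.

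If the sponsor wants the list-only count as the main one, SAP 4.4.1.1 should say so, SAP 4.7 should declare it as a change from the protocol, and off-list investigator pIMDs should be listed separately. That would be transparent, but it would leave the endpoint narrower than the protocol's definition, so the combined rule is preferable.

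The cost is one sentence, one derivation and one listing column, using data already collected. The downside is that some open-label investigator judgment enters the count, which the source column makes visible.
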